A different pattern was seen in peripheral tissues (fat and muscle), however. When we assessed insulin's ability to suppress lipolysis by quantifying the decrease in non-esterified fatty acid (NEFA) during the first insulin infusion step, it was evident that control and MODY2 cohorts had nearly total NEFA suppression while a much smaller decrease occurred in the T1DM group (figure 4D). Likewise, when muscle tissue was stimulated by a high insulin infusion (40 mU/m²/min) in the second step, control and MODY2 cohorts had similarly large increases in glucose disposal (R_d) above baseline, while a smaller increase was seen in T1DM (figure 4E). Multivariable linear regression showed insulinemia, but not glycemia, was significantly associated with muscle insulin sensitivity.

[figure not shown]

Figure 4: Preliminary Data

These data support the proposed concept that local tissue hyperinsulinemia, as occurs at muscle and fat in T1DM, but not in MODY2 nor control, nor any group at liver, is associated with tissue-specific IR. Despite having hyperglycemia, MODY2 participants had no more IR than control at any tissue. On the other hand, the addition of chronic peripheral hyperinsulinemia onto hyperglycemia in the T1DM group was associated with IR in muscle and fat tissue. The key conclusion is that local tissue hyperinsulinemia, rather than hyperglycemia, is the dominant contributor to tissue-specific IR in T1DM.

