5.3 Randomization

STUDY1-7 (Aims 1-2), include a longitudinal study of newly diagnosed T1DM patients during the first twelve months after diagnosis (T1DM SUBSTUDY, STUDY1-3) Because of the longitudinal nature of the T1DM substudy, no randomization process is needed for STUDY 1-3. The CONTROL SUBSTUDY investigates the effect of small doses of insulin in healthy, nondiabetic individuals over differing durations: one week (STUDY 5), one night (STUDY 6), both one week and one night (STUDY 7), and with no exogenous insulin at all (STUDY 4). Control participants will go through STUDY 4-7 in a random order. The study team will randomize participant into a treatment order group using a web-based randomization tool (<http://www.sealedenvelope.com>), a Microsoft Excel macro, or a randomization tool within Redcap.

STUDY B-C (Aim 3), is a random-order, 2x2 crossover study. On one arm, participants will consume a low-carbohydrate diet (LCD). On the other arm, participants will consume a standard carbohydrate diet (SCD). As shown in [figure 3](#), T1DM and control participants will be randomized into one of two treatment orders (“A” vs. “B”).

Random permuted blocks with a fixed size of 4 will be used to randomize patients into treatment order A (SCD then LCD) vs. treatment order B (LCD then SCD). The study team will randomize participant into a treatment order group using a web-based randomization tool (<http://www.sealedenvelope.com>), a Microsoft Excel macro, or a randomization tool within Redcap.

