7.1 Hyperinsulinemia

The hyperinsulinemic, euglycemic clamp exposes participants to high insulin levels, potentially leading to hypoglycemia and hypokalemia. As shown in figures 6 and 8, the insulin infusion rate during the clamp will be 40 mU/m²/min. This infusion rate is anticipated to result in plasma insulin concentrations between 50 and 130 μ U/mL,(64, 65) levels that are within the range of physiological hyperinsulinemia and comparable to concentrations seen after meal ingestion.(65-67) By comparison, the most commonly used insulin infusion rate in the treatment of diabetic ketoacidosis is 0.1 U/kg/hr.(56) In a 70 kg, 1.73 m² individual, this infusion rate would equal 67 mU/m²/min, over 50% higher than the 40 mU/m²/min rate used in this study.

Nondiabetic CONTROL SUBSTUDY participants will be exposed to low levels of iatrogenic hyperinsulinemia from low doses of insulin glargine (STUDY 6-7)

and overnight IV regular insulin infusions prior to STUDY visits (STUDY 5 and 7). The insulin glargine dose of 0.2 u/kg/day was selected to induce long-term (7 days) iatrogenic hyperinsulinemia while avoiding the confounding effect of hypoglycemia. Based on a previous pharmacokinetic-pharmacodynamic study of glargine, this dose is anticipated to drop fasting plasma glucose by no more than 10 mg/dL.(68) Because insulin glargine is a long-acting insulin analog, we do not anticipate it will cause a rapid drop in plasma glucose concentrations, but rather a slow decrease over the course of hours. For short-term hyperinsulinemia, participants will receive intravenous (IV) regular insulin at 8 mU/m²/min for 8 hours overnight preceding the STUDY visit. Based on my previous research, I anticipate this dose will raise fasting plasma insulin concentrations in CONTROL SUBSTUDY participants from ≈8 µU/mL to ≈21 µU/mL, matching the average fasting insulin concentration of T1DM SUBSTUDY participants.(69)

We will use the following safety provisions to minimize risk of hypoglycemia and hypokalemia:

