10.0 Statistical Considerations

10.1 STUDY 1-7 (Aims 1-2)

10.1.1 Sample Size Justification

My accrual goal is to obtain an adequate number of participants within both the T1DM SUBSTUDY (STUDY 1-3) and CONTROL SUBSTUDY (STUDY 4-7) to ensure greater than 80% statistical power ($1-\beta$) for a two-sided α -level of 5% for each specific aim's primary outcome. The sample size calculations used the best-available previously published descriptions of insulin sensitivity(28, 105) and %FMD(7, 30, 106-108) in T1DM. Table 7 summarizes these calculations.

Table 7: Key parameters for sample size calculations for T1DM and CONTROL substudies. n , δ , $1-\beta$, σ , and r represent the sample size, the expected minimum difference, statistical power, overall standard deviation, and longitudinal correlation, respectively, for each key outcome. * indicates calculations based on preliminary data as previously described. [†] The detectable differences for GIR of 1.3 to 2.2 mg/kg/min represent a 20% to 21% change in outcomes. [‡] The detectable differences for %FMD of 2.2% to 4.3% represent a 25% to 39% change in outcomes.

Aim	T1DM Substudy					Control Substudy						
	Key Outcome for Power Calculation	n	δ	$1-\beta$	σ	r	Key Outcome for Power Calculation	n	δ	$1-\beta$	σ	r
1	GIR between STUDY T ^{LO} vs. T ^{HI} in mg/kg/min	20	1.3	0.88	2.7	0.79	GIR between STUDY C ^{BOTH} vs. C ⁰ in mg/kg/min	20	2.2	0.92	3.5	0.79
2	%FMD between STUDY T ^{LO} vs. T ^{HI}	20	2.2%	0.88	4.3%	0.83	%FMD between STUDY C ^{BOTH} vs. C ⁰	20	4.3%	0.83	3.7%	0.83

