10.1.2 Analysis Plan

The correlation between the independent variable TDD_{insulin} (averaged over 7 days prior to each STUDY visit) and the key dependent variable for each objective will be determined: GIR in Aim 1; %FMD and MVR in Aim 2. Several other explanatory variables could influence each specific aim's key dependent variable, however. For example, confounding variables might include hyperglycemia, hyperlipidemia, or the dependent variables in each aim could affect one another (e.g. insulin resistance could affect endothelial dysfunction). For this reason, I will use multivariable linear regression analysis to account for the effect of potential confounders, which include age, T1DM duration, glycemia (both from both CGM over 7 days and HbA1c), lipidemia (i.e. lipoprotein subclass sizes and particle concentrations), NEFA concentration, hypertension, BMI, body composition, and estrogen level.

The study accrual of 40 participants provides 3 to 4 degrees of freedom for a multivariable linear regression analysis. (i.e. TDD_{insulin} and 3 additional independent variables can be included in an adequately-powered model). To quantify the effect of potential confounders, unadjusted and adjusted linear regression models will be fit and compared for each Aim's primary outcome (GIR and %FMD). I will analyze changes in β -coefficients between unadjusted and adjusted models for scientifically significant differences.

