10.2 STUDY B-C (Aim 3)

10.2.1 Sample size justification

My accrual goal for STUDY B-C is to have a sufficient sample size to conduct multivariable linear regression with 4 degrees of freedom to quantify the effect of the independent variable, mean $TDD_{insulin}$, on the dependent variable, GIR during the last 30 minutes of the clamp study. At a minimum, 10 participants are needed per degree of freedom to conduct this analysis, thus, we will study 30 participants with T1DM and 10 control participants who are otherwise healthy.

Based on Del Prato et al.,(27) I anticipate participants completing the SCD arm will not see a change in GIR during the last 30 minutes of the clamp study compared to baseline, but will see an increase in GIR of at least 0.6 mg/kg/min after completing the LCD arm. This study also suggests the pooled standard deviation of GIR will be 0.8 mg/kg/min. If the true difference in the Δ GIR between LCD and SCD arms for the 30 T1DM participants is 0.6 mg/kg/min, we will be able to reject the null hypothesis that the difference is zero with probability (power) 0.976. The type 1 error probability associated with this test of this null hypothesis is 0.05.

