10.2.2 Analysis Plan

The correlation between the independent variable $TDD_{insulin}$ (averaged over 7 days prior to each STUDY B-C visit) and the GIR over the last 30 minutes of the clamp will be determined. Several other explanatory variables could confound this bivariate analysis, however. For example, confounding variables might include treatment order, hyperglycemia, hyperlipidemia, or measures of glycemic variability. For this reason, as with STUDY 1-5, I will use multivariable linear regression analysis to account for the effect of these potential confounders.

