10.2.4 Interim assessment

I will make one interim assessment after reaching one-half of the target accrual for the T1DM and control participants. Using Obrien-Fleming bounds for each aim's primary analysis with a two-sided test with α -level of

5%, a critical z-value of 2.80 (corresponding to a p-value of 0.0051) will be used to end the study at interim analysis. We will analyze our study's variance and adjust the sample size if needed.

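### In the randomised comparisons (STUDY 4-7 and STUDY B-C), variables measured after assignment are treated as confounders, so the adjusted coefficient is not the effect of the assigned insulin or diet

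*Combined protocol and SAP*

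**What the plan says.** Section 10.1.2 relates average total daily insulin dose (TDD) over the seven days before each visit to GIR, %FMD and microvascular recruitment. It then adjusts by multivariable regression for potential confounders that include "glycemia (both from both CGM over 7 days and HbA1c), lipidemia (i.e. lipoprotein subclass sizes and particle concentrations), NEFA concentration". TDD plus three covariates may enter; which three is not fixed. Unadjusted and adjusted models are to be compared, and the change in the coefficients is taken to quantify confounding. The section also raises the possibility that one aim's outcome influences the other's.

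These regressions cover randomised and non-randomised data. For controls, Section 5.3 says: "Control participants will go through STUDY 4-7 in a random order". The same section says that STUDY 1-3 needs no randomisation.

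For the randomised diet crossover, Section 10.2.2 starts from the correlation of TDD with GIR and then says "confounding variables might include treatment order, hyperglycemia, hyperlipidemia, or measures of glycemic variability", to be handled by the same kind of regression. Specific Aim 3 in Section 2.0 gives the goal as a reduction in insulin resistance adjusted for covariates.

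Neither analysis section says whether the unadjusted or the adjusted model is primary. The interim rules in 10.1.4 and 10.2.4 nevertheless act on each aim's "primary analysis with a two-sided test with α -level of" 5%.

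**The concern.** A confounder influences both the exposure and the outcome. Under random order, a variable recorded during or after the assigned condition cannot have determined that condition, but it can be changed by it. Adjusting for such a variable takes out whatever part of the effect passes through it, with either sign. It can also introduce bias through unmeasured causes shared by the covariate and the outcome.

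The protocol itself expects two of the listed variables to respond to insulin. Section 7.1 says of the glargine given to controls that "this dose is anticipated to drop fasting plasma glucose by no more than 10 mg/dL", and Section 3.0 uses the fall in NEFA as a measure of insulin action. A change in the coefficient cannot tell confounding from mediation. A reader told that it measures confounding could conclude that insulin's effect is smaller, or larger, than the randomised comparison shows.

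**Working it through.** **Timing, STUDY 4-7.** Glargine or placebo is injected for the seven days before the visit (6.1.1.6, 6.1.2). Home glucose monitoring covers that same week (6.1.1.4). Saline or insulin then runs overnight (6.1.3.3, 6.1.3.4). Basal NEFA and lipoproteins are drawn the next morning after FMD (6.1.3.8), and again late in the clamp (6.1.3.10). All therefore follow assignment, and the bloods also follow the Aim 2 outcome. HbA1c is different: 6.1.1.3 takes it at screening.

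**Timing, STUDY B-C.** Bloods are drawn at the visit that ends the diet week, after FMD (6.2.3.3). Section 10.2.2 does not restrict the glycemic and lipid covariates to values from before randomisation. TDD over the seven days before the visit is also recorded after assignment; the Figure 7 caption expects it to be one third lower on the low-carbohydrate diet.

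**The plan's own power figures.** These are for simple two-condition contrasts. With n pairs, difference δ and SD of the within-person difference s, the test statistic is δ/(s/√n), referred to the noncentral t, two-sided 5%.

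- Aim 3 (10.2.1): δ 0.6, n 30, s 0.8. 0.6/(0.8/√30) = 4.11, power 0.978 against the stated 0.976. It reproduces.
- T1DM GIR (Table 7): δ 1.3, n 20, SD 2.7, r 0.79. s = 2.7·√(2·0.21) = 1.75, power 0.883 against 0.88. It reproduces.
- Control GIR (Table 7): δ 2.2, n 20, SD 3.5, r 0.79. s = 3.5·√(2·0.21) = 2.268, SE = 2.268/√20 = 0.507, ratio 4.34, power 0.984. The printed 0.92 does not reproduce. The table may have been damaged in reading, so nothing rests on that.

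No power is given for an adjusted model.

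**Illustration for control GIR, adjusting for one covariate measured after assignment.** Assume that the condition shifts the covariate by k, in SDs of its within-person change, and that a share m of the 2.2 passes through it. Regress the within-person GIR difference on the covariate difference; the intercept is the adjusted effect.

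- Expected coefficient: 2.2·(1 − m)
- Covariate slope: b = m·2.2/k
- Residual SD: √(2.268² − b²)
- SE ≈ residual SD·√(1 + k²)/√20

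| k | m | Coefficient | SE | Ratio | Power (simulated) |
|---|---|---|---|---|---|
| 0.5 | 0 | 2.20 | 0.567 | 3.88 | 0.94 |
| 0.5 | +25% | 1.65 | 0.496 | 3.33 | 0.86 |
| 0.5 | −25% | 2.75 | 0.496 | 5.55 | >0.99 |
| 1 | 0 | 2.20 | 0.717 | 3.07 | 0.79 |
| 1 | +25% | 1.65 | 0.696 | 2.37 | 0.59 |
| 1 | −25% | 2.75 | 0.696 | 3.95 | 0.93 |

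With m = 0 the loss comes only from collinearity. At k = 0.5 and m = ±25%, the SE (0.496) is slightly below the unadjusted 0.507, because the covariate then explains enough outcome variance to offset the collinearity.

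**The same model for Aim 3** (unadjusted 0.978), at k = 0.5 and k = 1: m = 0 gives power 0.93 and 0.78; m = +25% (coefficient 0.45) gives 0.80 and 0.56; m = −25% (coefficient 0.75) gives 0.99 and 0.93.

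**The case against.** The strongest reply is that the unadjusted estimate is kept. Section 10.1.2 fits both models, 10.2.2 begins with the bivariate correlation, and Table 7 is powered on condition contrasts. Section 2.0 also frames the hypothesis as an independent association, so separating insulin from glycemia is part of the question. That is a fair reason to run the adjusted models. It does not justify reading their difference as confounding, and it does not say which estimate the conclusion or the interim rule uses.

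A reader might infer something stronger: that every regression in the plan removes real treatment effect and loses power. The documents do not support this, for five reasons.

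- STUDY 1-3 is observational, and glycemia and lipids may be genuine confounders there. The 40 participants counted in 10.1.2 include that group.
- The direction is not established. If high glucose or NEFA lowers GIR, insulin's lowering of them works against its harmful effect, and adjustment enlarges the coefficient.
- The lists are candidate pools. Only three covariates enter with TDD, HbA1c is taken at screening, 10.2.2 does not name NEFA, and the other aim's outcome is mentioned as an influence but is not in the covariate list.
- Controls may use capillary meters (6.1.1.4), so 7-day CGM may not exist for them.
- No passage gives the size of any covariate shift. The expected fall in fasting glucose is small, and the NEFA evidence comes from a clamp step in another study.

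These limits stand. They narrow the point to the randomised comparisons and make its numerical size conditional.

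**Conclusion.** The point holds for STUDY 4-7 and STUDY B-C. There the candidate confounders include variables that the assigned insulin or diet can change, so an adjusted coefficient is not the total effect of the assigned condition, and the change in beta cannot be called confounding. The bias may go either way. Precision falls when the condition shifts the covariate and the covariate explains little outcome variance.

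Under the assumed values, the control GIR coefficient moves from 2.2 to 1.65 or 2.75, and power from 0.98 to between 0.59 and over 0.99. This range rests on one covariate, shifts of 0.5 to 1 SD, mediated shares of −25% to +25%, and a paired-contrast model simpler than the planned TDD regression. It shows how much could change; it does not predict what will happen.

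Aim 3 has a further difficulty. What is randomised is the diet, and TDD is a response to it. Even the unadjusted TDD slope is therefore not the randomised diet effect, although the low- versus standard-carbohydrate contrast is what 10.2.1 powers.

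**What to change.** In 10.1.2 (for STUDY 4-7) and 10.2.2, name as primary the within-person contrast by randomised condition, with terms for participant and for visit order or period. In Aim 3 this is the low- versus standard-carbohydrate contrast. State that this analysis also governs the interim rules in 10.1.4 (for STUDY 4-7) and 10.2.4.

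For these comparisons, move CGM glucose, NEFA, lipoproteins, glycemic variability, the other aim's outcome and the Aim 3 TDD slope to secondary mediation or association models. Do not describe the change in beta as confounding. Leave covariate adjustment in STUDY 1-3, and HbA1c taken at screening, as planned. A screening value is constant within a participant and does not alter a within-person contrast.

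The cost is analysis-plan wording, with no new data or visits. The price is that, in the randomised parts, the independent association becomes a secondary result.

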7.5.1 Justification and rationale for inclusion of adolescent subjects with T1DM

The atherosclerotic changes of macrovascular disease in T1DM (e.g. increasing carotid intima media thickness) appear to begin in childhood and adolescence(80, 81) and morbidity and mortality risk is staggeringly high in younger adults.(10) As an example, among individuals ages 1-39, the standardized mortality risk (i.e. ratio between the observed number of deaths in a study population and the number of deaths that would be expected) for ischemic heart disease death is 8.9 (95% CI 6.2–12.9) in males and an astounding 41.7 (95% CI 28.9–58.2) in females. Thus, it is clear that pathophysiologic mechanisms that contribute to macrovascular

disease are operative *early in the natural history of T1DM*. These same early pathophysiologic mechanisms have not been identified, however.

To date *only one study* has examined pediatric T1DM patients with typical glycemic control, which found that adolescents were 37% less insulin sensitive than matched control subjects,(9) *suggesting that exposure to insulin resistance begins early in the natural history of T1DM*.

To determine the root cause of T1DM insulin resistance and translate this information into therapies that would ameliorate insulin resistance in T1DM and its contribution to macrovascular disease, the endocrine and molecular mechanisms causing insulin resistance must be assessed early in the disease duration. This is because:

- 1) T1DM insulin resistance appears to begin early in the disease process.(9, 28)
- 2) The incidence of T1DM onset is highest between ages 10-14.(82)
- 3) At younger ages and shorter disease durations there are minimal confounding covariables that would contribute to insulin resistance at a molecular level. These confounding covariables include co-morbidities associated with T1DM such as diabetic nephropathy,(83) prolonged exposure to hypertriglyceridemia,(84, 85) excessive BMI(86, 87) and visceral adiposity,(88, 89), deleterious effects of aging and progressive inflammation on extracellular matrix remodeling,(90, 91) and increasing age per se.(92, 93)

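### The insulin-dose regressions reach 4 degrees of freedom only by counting T1DM and control participants together, yet no diabetes-status term is required

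*Combined protocol and SAP*

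**What the plan says.** **Aim 3 (10.2.1).** The accrual goal is a regression of glucose infusion rate (GIR) on mean total daily insulin dose with 4 df. The rule is "At a minimum, 10 participants are needed per degree of freedom to conduct this analysis", and the section meets it this way: "we will study 30 participants with T1DM and 10 control participants who are otherwise healthy". The power statement that follows, "we will be able to reject the null hypothesis that the difference is zero with probability (power) 0.976", is for the 30 T1DM participants alone.

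**Aims 1-2 (10.1.2).** "The study accrual of 40 participants provides 3 to 4 degrees of freedom for a multivariable linear regression analysis", which the plan explains as dose plus three other variables. Sections 2.0 and 6.1 give 20 participants in the T1DM substudy and 20 in the control substudy. Section 10.1.2 does not say that the two are pooled, does not state the 10-per-df rule, and follows a Table 7 that powers each substudy separately.

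**Covariates.** Section 10.1.2 names candidate confounders, "which include age, T1DM duration, glycemia (both from both CGM over 7 days and HbA1c", then lipids, blood pressure, body size and others. It adds that "unadjusted and adjusted linear regression models will be fit and compared", with the change in coefficients to be interpreted. Section 10.2.2 says "confounding variables might include treatment order, hyperglycemia, hyperlipidemia, or measures of glycemic variability". Both lists are open, neither names diabetes status, and no covariate is mandatory.

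**The concern.** The two groups sit at different doses and may differ in insulin sensitivity for reasons other than current dose. In Aims 1-2, controls inject 0 or 0.2 units/kg/day, while T1DM participants enter visits at 0.4-0.6, at most 0.4, and at least 0.6 (sections 6.1, 6.1.2). Section 3.0 reports lower muscle insulin sensitivity in T1DM, and section 7.5.1 cites a study that "found that adolescents were 37% less insulin sensitive than matched control subjects". The plan attributes that gap to insulin exposure, but that is the hypothesis under test.

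A pooled regression without a status term lets the dose slope absorb the whole group difference, in the direction of the hypothesis. Section 10.1.2 reads the contribution of hyperinsulinemia from this slope and from how it changes on adjustment. A dose effect could be reported where there is none, or a real one overstated. If the groups are instead fitted separately, the stated model size no longer follows from the participants available.

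**Working it through.** **1. The plan's df count.** At 10 participants per df:

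- Aim 3: (30 + 10)/10 = 4, as stated; T1DM only, 30/10 = 3.
- Aims 1-2: (20 + 20)/10 = 4, the top of the stated 3 to 4; T1DM only, 20/10 = 2.

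The figure of 4 is reproduced only with controls counted.

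**2. The Aim 3 power figure.** A two-sided paired t-test with n = 30, difference 0.6, SD of differences 0.8 and alpha 0.05 gives 0.978 against the stated 0.976. So 0.8 acts as the SD of paired differences. The matching SD of a single GIR value is 0.8/sqrt(2(1 - r)): 0.8 at r = 0.5, and 0.8/sqrt(0.42) = 1.23 at r = 0.79 (the GIR correlation in Table 7).

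**3. Bias of a pooled least-squares slope in Aim 3 with no true dose effect.** Let p be the share of visits from T1DM participants, D the difference in mean dose, and W the average within-group dose variance. Then slope = -gap x p(1-p)D / [p(1-p)D² + W]. Assume doses of 0.6 and 0.4 in T1DM (one third lower on the low-carbohydrate diet, figure 7 legend) and 0 in controls. Then p = 60/80, D = 0.5 and W = 0.75 x 0.01 = 0.0075, so slope = -gap x 0.09375/0.054375 = -1.72 at a gap of 1 mg/kg/min. The slope implied by 10.2.1 under these doses is 0.6/0.2 = 3.0 in size, so the bias is 1.72/3.0 = 57% of it. With between-person dose spread (SD 0.15) the slope is -5.69 at gap 4, hence -1.42 at gap 1, or 47%. A status term returns it to 0.

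**4. False-positive rates, Aim 3** (simulation, true dose effect 0, nominal 5%). Assumed: T1DM dose 0.6 (SD 0.15) on the standard diet and one third lower on the other, control dose 0, HbA1c 7.2 (0.8) against 5.0 (0.3). Least-squares fits use person-clustered standard errors, and those with HbA1c also include treatment order.

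| Gap 1 mg/kg/min | Least squares, unadjusted | Least squares, HbA1c | Within-person weighting, unadjusted | Within-person weighting, HbA1c |
|---|---|---|---|---|
| SD 0.8, r 0.5 | about 91% | about 40% | about 78% | about 28% |
| SD 1.23, r 0.79 | about 54% | about 20% | about 27% | about 9% |

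With a status term the rates are roughly nominal, 5-10%. At a gap of 0.5, least squares gives 39-40% and 16% (SD 0.8), or 19-20% and 10-11% (SD 1.23).

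**5. False-positive rates, Aims 1-2.** SDs 2.7 and 3.5 and r = 0.79 come from Table 7, and HbA1c 6.6 (0.5) against 4.8 (0.4) from section 3.0. The largest gap is anchored to the documents: 1.3/0.20 = 6.5 mg/kg/min as T1DM mean GIR (Table 7 note), and 6.5 x 0.37/0.63 = 3.8. It is then halved and quartered, because newly diagnosed patients may differ less. T1DM doses are assumed uniform within 0.4-0.6, 0.2-0.4 (or 0.35-0.4) and 0.6-0.8. Controls have 0 or 0.2, plus about 0.014 where the overnight infusion is given.

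| Gap | Least squares, unadjusted | Least squares, HbA1c | Random intercept, unadjusted |
|---|---|---|---|
| 3.8 | 98% | 36-39% | about 33% |
| 1.9 | 53% | 13-15% | about 12% |
| 0.95 | 16-19% | 7-8% | about 8% |

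With a random intercept and HbA1c the rate is 5-7%. Under least squares it is 4-6% with a status term and 5-6% in T1DM only. At gap 3.8 the mean unadjusted slope shrinks from -6.46 to -1.28 with the random intercept. Table 7's target over an assumed dose difference of 0.40 is 1.3/0.40 = 3.25, so the remaining bias is 1.28/3.25 = 39% of the target.

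**6. T1DM duration as a covariate.** It has no value in controls. A complete-case adjusted model would drop all 20, so a 40-person unadjusted slope would be compared with a 20-person adjusted one. Coded 0 in controls, it becomes a partial proxy for status.

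**7. What controls add in Aim 3.** If their dose is 0 on both diets, they have no within-group dose variation. Once status is in the model, the dose slope rests on the 30 T1DM participants: with no other covariates the status-adjusted and T1DM-only slopes are identical.

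**The case against.** **Pooling is inferred.** Table 7 powers the substudies separately, T1DM duration makes sense only in T1DM, and section 2.0 gives controls their own four-condition question. For Aim 3, section 2.0 describes a crossover in adults with T1DM, Table 2 requires a pump and HbA1c of 5.6-9.0%, and no control dose is defined; if it is missing, a complete-case fit is T1DM-only. This stands, and it makes the point conditional. But 10.2.1 counts the controls toward the regression, section 5.3 randomises them to diet order, and without them the 4 df is not reached.

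**The repeated visits matter more than pooling in Aims 1-2.** This also stands: most of the inflation there comes from ignoring within-person correlation. Section 10.1.2 says only linear regression, so least squares is a fair literal reading, but not the only one. In Aim 3 within-person weighting reduces the problem without removing it.

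**The plan already regards the unadjusted model as confounded, and its open lists permit a status term.** Both are true. Permission is not a requirement, though, and the change from unadjusted to adjusted slope is itself a planned result.

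**Ten per df is a rule of thumb**, written only for Aim 3, and each T1DM-only fit would have 60 visits (20 x 3 or 30 x 2). No harm from 4 df in such a fit has been shown; restating the number is a matter of consistency with the plan's own rule.

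**Stronger readings.** A reader might infer that the plan definitely pools in Aims 1-2, that the trial carries a 98% false-positive rate, or that its powered comparisons fail. The documents support none of these. Pooling is not stated there. The 98% belongs to one unadjusted model that ignores within-person correlation, at the largest assumed gap. The paired contrasts behind Table 7 and the Aim 3 power figure do not use the pooled slope, although 10.1.2 and 10.2.2 do not list them as the analysis.

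**Conclusion.** The concern holds conditionally and is strongest in Aim 3. Either the groups are pooled and nothing requires the term that separates dose from diabetes, or they are not and the stated 4 df should be restated.

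If pooled, the Aim 3 false-positive rate at a gap of 1 mg/kg/min is about 20-40% with HbA1c under least squares and about 9-28% with within-person weighting. In Aims 1-2 the inflation is large under least squares but close to nominal with HbA1c and a random intercept.

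All rates rest on an assumed group gap treated as unrelated to dose, on assumed doses and, in Aim 3, on a control dose of 0. The direction of the bias holds whatever the size of the gap, provided T1DM participants are the less insulin-sensitive group, as sections 3.0 and 7.5.1 report. This should be fixed before analysis; confidence is medium, because the plan leaves the pooling decision open.

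**What to change.** In 10.1.2 and 10.2.1-10.2.2, state whether the groups are pooled, and choose one route:

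- (a) Fit the dose regression in T1DM participants only, and restate model size as 3 df in Aim 3 (dose plus two covariates) and 2 df in Aims 1-2 (dose plus one). This matches Aim 3's stated question, which is about T1DM.
- (b) Pool, with a mandatory diabetes-status term in every model, including the unadjusted one. That leaves dose, status and two covariates. Omit T1DM duration from pooled models and state what dose value controls receive in the regression.

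Under either route, model within-person correlation with a random participant intercept or equivalent, and fit the compared unadjusted and adjusted models on the same participants.

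The cost is wording and one or two fewer covariates per model; no new data are needed. Route (b) in Aims 1-2 also assumes the same dose slope in both groups. Analysing the control substudy by randomised condition is a separate recommendation.
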